5.4 Study Rationale

The purpose of this randomized, placebo-controlled study is to confirm the efficacy and safety of terlipressin in the treatment of subjects with HRS Type 1 to provide data to support regulatory approval of the New Drug Application (NDA). Efficacy will be assessed through the primary endpoint of verified HRS reversal; other important efficacy parameters will be assessed including short-term durability of verified HRS reversal, magnitude of SCr lowering effect and effects in important subgroups (eg, systemic inflammatory response syndrome [SIRS] subgroup). Safety data will be collected and incorporated into the overall safety assessment of terlipressin. Methodological obstacles encountered in the REVERSE trial that reduced its ability to show statistical significance on the primary endpoint have been addressed in this trial design.

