8.4 Exclusion Criteria

If any of the following exclusion criteria are met, the subject will **not** be enrolled:

- 1. Serum creatinine level greater than 7.0 mg/dL.
- 2. At least 1 event of LVP at least 4 L within 2 days of randomization.

Note: The investigator must review any paracentesis performed in the pre-enrollment period and volume status after paracentesis must be considered carefully; as per standard of care, adequate replacement of fluid removed with albumin is required.

3. Sepsis and/or uncontrolled bacterial infection (eg, persisting bacteremia, persisting ascitic fluid leucocytosis, fever, increasing leucocytosis with vasomotor instability).

Note: Sepsis is defined as documented active, untreated infection and presence of SIRS. SIRS is defined as the presence of 2 or more of the following findings: temperature greater than 38°C or less than 36°C; heart rate greater than 90/min; respiratory rate greater than 20/min or partial pressure of arterial carbon dioxide (PaCO₂) less than 32 mm Hg; white blood cell (WBC) count greater than 12,000 cells/μL or less than 4,000/ μL).

Note: Patients with decompensated liver disease frequently have SIRS criteria in the absence of uncontrolled infection or sepsis. Subjects with SIRS criteria, in the absence of active, untreated infection, and reasonably attributed to decompensated liver disease or alternate causes (eg, hepatic hydrothorax, acute alcoholic hepatitis) should be enrolled after discussion with the sponsor via the Medical Hotline, assuming they meet all subject selection criteria.

- 4. Less than 2 days anti-infective therapy for documented or suspected infection.
- 5. Shock.

Note: Shock is defined as hypotension (MAP less than 70 mm Hg or a decrease greater than 40 mm Hg in systolic blood pressure from baseline) with evidence of hypoperfusion abnormalities (eg, peripheral cyanosis, hypothermia, marked asthenia, pallor, obtundation not attributable to hepatic encephalopathy).

6. Current or recent (within 4 weeks) treatment with or exposure to nephrotoxic agents: eg, aminoglycosides, amphotericin, cyclosporine A, cisplatin, nonsteroidal anti-inflammatory drugs (NSAIDs: eg, ibuprofen, naproxen, diclofenac), significant exposure to radiographic contrast agents (large doses or multiple injections of iodinated contrast media, eg, during coronary or abdominal angiogram.

Note: Up to 3 doses of an NSAID within the prior month is acceptable.

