13.4 Detail of Safety Assessments and Procedures

13.4.1 Vital Signs

Vital sign measurements will be recorded at baseline (with the physical examination), during study drug administration, at the end of treatment, and at the Day 30 follow-up.

Systolic and diastolic blood pressure and heart rate will be recorded at baseline, and pre-dose and post-dose at 5 minutes (\pm 2 min) and 2 hours (\pm 0.25h) for every dose.

Body temperature, respiratory rate, and pulse oximetric saturation (SpO₂) will be recorded once daily at baseline and during study drug administration.

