15.3.6.2 Secondary Efficacy Analyses

A Hochberg procedure for multiple testing and the alpha level corresponding to the Z score of the primary efficacy analysis will be used for testing the secondary efficacy analyses at either the interim analysis or the final analysis.

If the interim analysis for the primary endpoint is successful then the secondary efficacy analyses will be tested against a corresponding p-value of 0.005166 for a Z score of 2.79651. The p-values from the 4 secondary efficacy analyses will be ordered from largest to smallest and will be compared as in Table 15–3 below:

Table 15–3: Multiple Testing for the Interim Analysis of the Secondary Efficacy Analyses

p-value Ordering	α Comparator	If p-value less than α then:	If p-value at least α then:
Largest p- value	0.005166 = 0.005166/(4 - 4 + 1)	All 4 analyses are significant	Test the second largest p-value
Second largest p-value	0.002583 = 0.005166/(4 - 3 + 1)	The remaining 3 analyses are significant	Test the third largest p-value
Third largest p-value	0.001722 = 0.005166/(4 - 2 + 1)	The remaining 2 analyses are significant	Test the smallest p-value
Smallest p- value	0.001292 = 0.005166/(4 - 1 + 1)	This analysis is significant	No analyses are significant

If the interim analysis for the primary endpoint is not successful then the study will continue onto the final analysis. If the primary efficacy analysis is successful, then the secondary efficacy analyses will be tested against a corresponding p-value of 0.047993 for a Z score of 1.97743, as shown in Table 15–4 below:

Table 15–4: Multiple Testing for the Final Analysis of the Secondary Efficacy Analyses

p-value Ordering	α Comparator	If p-value less than α then:	If p-value $\geq \alpha$ then:
Largest p- value	0.047993 = 0.047993/(4 - 4 + 1)	All 4 analyses are significant	Test the second largest p-value
Second largest p-value	0.023997 = $0.047993/(4 - 3 + 1)$	The remaining 3 analyses are significant	Test the third largest p-value
Third largest p-value	0.015998 = 0. 047993/(4 - 2 + 1)	The remaining 2 analyses are significant	Test the smallest p-value
Smallest p- value	0.011998 = 0. 047993/(4 - 1 + 1)	This analysis is significant	No analyses are significant

[figure not shown]
The following are the secondary endpoints:

[figure not shown]

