• Incidence of HRS reversal in the SIRS subgroup, defined as the percentage of SIRS subjects with HRS reversal. HRS reversal is defined as the percentage of subjects with a SCr value not more than 1.5 mg/dL while on treatment by Day 14 or discharge (SCr values after RRT, TIPS, liver transplant, or open-label vasopressor use will be excluded). This endpoint will be summarized by treatment group and analyzed similarly to HRS reversal. The SIRS subgroup is defined as any subject with at least 2 of the following criteria: WBC less than 4,000 or greater than 12,000 cells/μL; HR greater than 90 bpm; temperature greater than 38°C or less than 36°C; respiratory rate of greater than 20/min; HCO₃ less than 21 mmol/L; the latter criterion represents an approximation of the SIRS criterion PaCO₂ of less than 32 mm Hg, derived from the observed HCO₃ in subjects with HRS in whom a PaCO₂ value was available (from the TAHRS study) and the calculated HCO₃ in subjects with decompensated liver disease and PaCO₂ of less than 32 mm Hg.

Incidence of verified HRS reversal without HRS recurrence by Day 30. HRS Type 1 recurrence is defined in Section 10.5. Incidence of verified HRS reversal, defined as the percentage of subjects with 2 consecutive SCr values no more than 1.5 mg/dL at least 2 hours apart, while on treatment up to 24 hours after the final dose of study drug, by Day 14 or discharge. Subjects must be alive without RRT for at least 10 days after achieving verified HRS reversal. SCr values after RRT, transjugular intrahepatic portosystemic shunt (TIPS), liver transplant, or open-label vasopressor use will be excluded from primary end point analysis. SCr values obtained after midodrine administration will be included if midodrine was started on Day 1, was administered for no more than 24 hours, and the subject was enrolled on or after 17 August 2018. SCr values will also be included if obtained after the administration of a single dose of dobutamine. This endpoint will be summarized by treatment group and analyzed similarly to HRS reversal.

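### Does counting respiratory rate and bicarbonate as separate SIRS criteria undermine the tested SIRS-subgroup endpoint?

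*Combined protocol and SAP*

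**What the plan says.** Sections 13.6.2 and 15.3.6.2 give the same rule for the SIRS subgroup: "The SIRS subgroup is defined as any subject with at least 2 of the following criteria". The items are white cell count, heart rate, temperature, respiratory rate above 20/min and HCO3 below 21 mmol/L. Of HCO3, both sections say that "the latter criterion represents an approximation of the SIRS criterion" PaCO2 below 32 mm Hg, and they name the data from which the cut-off was derived.

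The note to exclusion criterion 3 in Section 8.4 defines sepsis and, for that purpose, says "SIRS is defined as the presence of 2 or more of the following findings". It lists four findings. The respiratory one is joint: "respiratory rate greater than 20/min or partial pressure of arterial carbon dioxide" below 32 mm Hg.

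HRS reversal in the SIRS subgroup is one of the four secondary endpoints under the Hochberg procedure of Section 15.3.6.2: "The p-values from the 4 secondary efficacy analyses will be ordered from largest to smallest". Section 5.4 cites the SIRS subgroup as an example of an important subgroup.

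**The concern.** The same term is counted in two ways within one protocol. If HCO3 stands in for PaCO2, then respiratory rate and HCO3 are two readings of what Section 8.4 treats as one respiratory finding. Counting both allows a subject with normal white cells, heart rate and temperature to reach the threshold of two on that finding alone. The visible text explains the HCO3 cut-off but not the separate counting.

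What is at stake is the label. A significant result in this formally tested endpoint would be reported as an effect in subjects with SIRS. If a sizeable part of the subgroup had one SIRS finding by the protocol's other rule, a reader might ask whether the result depends on them, and the visible text plans no analysis that would answer.

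**Working it through.** **The plan's own figures.** The plan states no size, prevalence or power for the SIRS subgroup, so there is no SIRS figure to reproduce. The significance level applied to the endpoint does reproduce: for the final boundary, 2 × (1 − Φ(1.97743)) = 0.047993, and the smallest Hochberg comparator is 0.047993 / 4 = 0.011998. Neither depends on how SIRS is counted.

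**Which subjects change.** Five yes/no items give 2^5 = 32 patterns.

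- At least 2 of 5: 32 − 1 (none abnormal) − 5 (exactly one abnormal) = 26 patterns qualify.
- With respiratory rate and HCO3 merged into one finding, at least 2 of 4: 25 qualify.
- The pattern lost is respiratory rate plus HCO3 with the other three items normal. No pattern moves the other way.

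Set against Section 8.4 as written, which uses measured PaCO2, the 26 patterns divide as follows:

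| Patterns | Number | Standing under Section 8.4 |
|---|---|---|
| At least 2 of white cells, heart rate, temperature, respiratory rate (11 combinations × 2 HCO3 states) | 22 | Met, whatever the PaCO2 |
| HCO3 plus exactly one of white cells, heart rate, temperature; respiratory rate normal | 3 | Met only if PaCO2 is in fact low |
| Respiratory rate plus HCO3 only | 1 | One finding, whatever the PaCO2 |

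Only the last row concerns the counting. The middle row concerns how well HCO3 approximates PaCO2, and merging the pair would leave it untouched.

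**How many subjects.** The documents give no prevalences, so every figure here is illustrative. Under independence,

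P(pair only) = P(RR) × P(HCO3) × (1 − P(WBC)) × (1 − P(HR)) × (1 − P(temp)).

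Narrower assumed ranges (WBC 30–40%, HR 30–35%, temperature 5%, RR 15–30%, HCO3 40–70%):

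- lowest: 0.15 × 0.40 × 0.60 × 0.65 × 0.95 = 2.2%, or 6.7 of 300
- highest: 0.30 × 0.70 × 0.70 × 0.70 × 0.95 = 9.8%, or 29.3 of 300
- as a share of the five-item subgroup, over all corners of these ranges: 5.4% to 18.0%

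Wider assumed ranges (WBC and HR 20–50%, temperature 2–10%, RR 10–40%, HCO3 30–70%):

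- lowest: 0.10 × 0.30 × 0.50 × 0.50 × 0.90 = 0.7%, or 2.0 of 300
- highest: 0.40 × 0.70 × 0.80 × 0.80 × 0.98 = 17.6%, or 52.7 of 300
- as a share of the subgroup: 1.4% to 35.9%

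Positive association between the two items raises the share. With an assumed odds ratio of 3, the narrower ranges give 8.5% to 21.6% of the subgroup.

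**What that does to the estimate.** Let s be the pair-only share, taken as equal in the two arms (as randomisation gives on average for a baseline characteristic). Let d1 be the treatment difference in the remaining members and d2 the difference in the pair-only members. The subgroup difference is (1 − s) × d1 + s × d2 = d1 + s × (d2 − d1). With s between 5.4% and 18.0%, the estimate moves by that fraction of the gap between d1 and d2. Nothing in the documents indicates the size or direction of that gap.

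**Validity of the test.** The rule uses no outcome data and is fixed in advance. Its two statements name no assessment time, but the natural reading is baseline, defined in Section 15.3.7 as the last available value before study drug. All five items exist then: for temperature and respiratory rate Section 13.4.1 says they "will be recorded once daily at baseline and during study drug administration"; for heart rate it says "Systolic and diastolic blood pressure and heart rate will be recorded at baseline"; HCO3 and the blood count are baseline tests in Sections 13.5.1.1 and 13.5.1.2. Membership so defined cannot be influenced by treatment.

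**The case for a change.** The best case for acting is that the pair-only pattern has one finding under Section 8.4 regardless of prevalence or the quality of the proxy, that the endpoint is confirmatory rather than descriptive, and that the check is nearly free: one repeat analysis outside the Hochberg procedure and one count per arm, from data already collected. The pair-only share could reach a third of the subgroup under the wider ranges. All of this is correct as far as it goes.

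Three things limit it. First, the two rules do different jobs. The Section 8.4 note helps a site decide whether a candidate is septic; the Section 15.3.6.2 rule selects an analysis population. No section says the second must follow the first. It could not be applied as written to every subject either, because PaCO2 is not among the laboratory assessments listed in Section 13.5.

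Second, the absence of a check cannot be asserted. The Amendment 2 summary places sensitivity analyses in Section 15.3.6.3, and the public text goes from 15.3.6.2 to 15.3.6.4. The summary mentions only the recurrence assumption, but it describes what was revised, not everything the section contains.

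Third, the proposed repeat would keep the five-item rule for the test and carry no inferential weight. It would also still rest on HCO3, so it says nothing about the larger group whose agreement with Section 8.4 depends on the proxy: 11.9% to 27.7% of subjects under the narrower ranges.

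What stands is that the plan could have said why the items are counted separately.

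**Conclusion.** No change follows. The inconsistency is real but confined to one of 26 qualifying patterns. The tested rule is explicit, stated the same way in two sections and possibly intended. It does not affect the significance level or favour either arm, provided membership is taken from pre-dose values, which is how an analyst would read Section 15.3.7.

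The number of subjects involved cannot be derived from the documents. The range of 0.7% to 17.6% of subjects rests wholly on assumed prevalences and independence, and it shows only that the share could be negligible or appreciable.

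A reader who wants to know can be given the count of pair-only subjects per arm, and a descriptive repeat with the pair merged, under Section 15.3.9, which allows additional non-inferential analyses. Neither would alter the tested population, the Hochberg decision or the primary conclusion, so an amendment would gain nothing.

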15.3.6.4 Safety Analyses

Continuous variables will be summarized by N, mean, standard deviation, median, minimum and maximum. These include:

- Change from baseline in MELD score.
- Change from baseline in encephalopathy score.
- Change from baseline in BUN.
- Daily values, daily averages, and change from baseline of vital signs of body temperature, systolic blood pressure, diastolic blood pressure, heart rate, respiratory rate, SpO₂, and MAP.
- Change from baseline in laboratory values.

Laboratory shift tables will be created.

Adverse events will be summarized by frequency and percentage of subjects.

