13.3.5 Assessment of Multi-Organ Dysfunction

With the advancement in intensive care medicine, multiorgan dysfunction syndrome (MODS) has replaced the term multiorgan failure since the completion of the REVERSE study. According to Al-Khafaji et al, 2015, MODS describes a continuum with incremental degrees of physiologic derangements in individual organs; a process rather than a single event. Alteration in organ function can vary widely from a mild degree of organ dysfunction to completely irreversible organ failure.

Multi-organ failure or dysfunction, a hallmark of acute on chronic liver failure (ACLF), common in the study patient population, is defined and quantified by the original CLIF-SOFA score or its simplified version Chronic Liver Failure Consortium (CLIF-C) Organ Failure score (Arroyo et al, 2015). The scoring system has been developed and validated for predicting mortality in patients with ACLF (Jalan et al, 2014).

Table 13–2 CLIF-C Organ Failure Score

Organ System	Score = 1	Score = 2	Score = 3
Liver, bilirubin (mg/dL)	< 6	6 to ≤ 12	> 12
Kidney, creatinine (mg/dL)	< 2	2 to < 3.5	\geq 3.5 or renal replacement
Brain, grade (West-Haven)	0	1 to 2	3 to 4
Coagulation, INR	< 2.0	2.0 to < 2.5	≥ 2.5
Circulation, MAP (mm Hg)	≥ 70	< 70	Vasopressors
Respiratory PaO ₂ /FiO ₂	> 300	\leq 300 and $>$ 200	≤ 200
or SpO ₂ /FiO ₂	> 357	$> 214 \text{ and} \le 357$	≤ 214

Source: Arroyo et al, 2015.

Abbreviations: FiO_2 = fraction of inspired oxygen; INR = international normalized ratio; MAP = mean arterial pressure; PaO_2 = partial pressure of arterial oxygen; SpO_2 = pulse oximetric oxygen saturation.

During baseline information collection and adverse event reporting, the investigators are required to record the actual organs involved in MODS (ie, other organs involved in MODS in addition to the baseline hepatic and renal dysfunction, and the severity of dysfunction in each organ involved), as well as MODS, itself, as a disease state. The use of the simplified version CLIF-C Organ Failure scoring system in documenting MODS organ involvement and MODS severity is strongly encouraged. Assessment of MODS will be detailed in the Site/Investigator Study Manual.

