13.4.2 Encephalopathy Score

Clinically detectable encephalopathy is to be assessed prior to study drug administration and daily during study drug administration using the clinical criteria described in Table 13–3.

Table 13–3 West Haven Criteria for Semiquantitative Grading of Mental State

Grade 1	Trivial lack of awareness.
	Euphoria or anxiety.
	Shortened attention span.
	Impaired performance of addition.
Grade 2	Lethargy or apathy.
	Minimal disorientation for time or place.
	Subtle personality change.
	Inappropriate behavior.
	Impaired performance of subtraction.
Grade 3	Somnolence to semi-stupor, but responsive to verbal stimuli.
	Confusion.
	Gross disorientation.
Grade 4	Coma (unresponsive to verbal or noxious stimuli).

Source: Ferenci et al, 2002.

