15.3.8 Missing Data

Unless otherwise stated, no imputation will be made for missing data.

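### Encephalopathy grade is summarized as a continuous change, so the planned output cannot show how many subjects per arm newly reached or worsened to grade 3-4

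*Combined protocol and SAP*

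**What the plan says.** Section 15.1 names the encephalopathy score as a safety variable in its own right, separate from adverse events.

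Section 13.4.2 sets the measurement: "Clinically detectable encephalopathy is to be assessed prior to study drug administration and daily during study drug administration", using Table 13-3. That table runs from grade 1 (first descriptor "Trivial lack of awareness") to grade 4 ("Coma (unresponsive to verbal or noxious stimuli"). It has no row for absence of encephalopathy.

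Section 15.3.6.4 sets the analysis. It opens with "Continuous variables will be summarized by N, mean, standard deviation, median, minimum and maximum" and then lists "Change from baseline in encephalopathy score" as one of those variables. Shift tables are planned for laboratory results and for nothing else. Adverse events are to be reported as counts and percentages of subjects. Section 15.3.8 adds that, unless otherwise stated, "no imputation will be made for missing data".

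Elsewhere the protocol does recognize a no-encephalopathy level. In Table 13-2 (Section 13.3.5) the row that begins "Brain, grade (West-Haven" has grade 0 as its lowest category, and Table 22-1 scores absence of hepatic encephalopathy as 0.

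**The concern.** A West Haven grade is an ordered category. The step from 3 to 4 is not the same quantity as the step from 1 to 0, and a mean change treats them as equal. For safety, the useful question is how many subjects in each arm reached a severe grade that they did not have at baseline. None of the six planned statistics answers it. The mean can be brought to zero by small improvements in other subjects. The median stays at zero whenever most subjects do not change. The maximum records that an event happened, not how often.

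At stake is the readability of one named safety variable that is collected daily during treatment. The study could hold the data that show an imbalance in severe encephalopathy and still publish a summary of the score in which the imbalance cannot be read.

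**Working it through.** The documents give no rate, power or expected change for the encephalopathy score, so there is no planned figure to reproduce. The counts below are assumptions that show how the planned statistics behave. Only the arm sizes (200 and 100, Section 15.3.1), the grades (Table 13-3, with 0 for none as in Table 13-2) and the list of statistics (Section 15.3.6.4) come from the plan.

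**One arm of 200, exact offset.** Let k subjects go to coma and m improve by one grade, with all others unchanged. Mean change = (k x rise - m) / 200. SD = square root of [(k x rise² + m) / 199] when the mean is 0.

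| Path to coma | k | m | Mean | Median | SD | Min | Max |
|---|---|---|---|---|---|---|---|
| 0 to 4 (rise 4) | 2 | 8 | 0.00 | 0 | 0.45 | -1 | +4 |
| 0 to 4 | 5 | 20 | 0.00 | 0 | 0.71 | -1 | +4 |
| 0 to 4 | 10 | 40 | 0.00 | 0 | 1.00 | -1 | +4 |
| 1 to 4 (rise 3) | 5 | 15 | 0.00 | 0 | 0.55 | -1 | +3 |

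For the second row: (5 x 4 - 20) / 200 = 0 and square root of [(5 x 16 + 20) / 199] = 0.71. From 2 to 10 comas (1% to 5% of the arm), the mean, median, minimum and maximum do not move. Only the SD changes, and it does not say in which direction or in how many subjects.

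**Two arms.** Take 10 comas and 40 one-grade improvements in 200 terlipressin subjects, against 1 coma and 4 one-grade improvements in 100 placebo subjects.
- Terlipressin: mean (40 - 40) / 200 = 0, median 0, range -1 to +4, SD 1.00.
- Placebo: mean (4 - 4) / 100 = 0, median 0, range -1 to +4, SD = square root of [(16 + 4) / 99] = 0.45.
- New coma: 10/200 = 5.0% against 1/100 = 1.0%. Apart from N, only the SD separates the arms.

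**No offset at all.** Five comas from grade 0 in 200 give a mean of 5 x 4 / 200 = 0.10. Twenty subjects worsening by a single grade also give 20 x 1 / 200 = 0.10. The median is 0 in both. The maximum differs (+4 against +1), but again without a count.

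**Coding of none.** Section 13.4.2 and Table 13-3 do not say how absence of encephalopathy is entered. If it were left blank and not imputed, a subject without encephalopathy at baseline would have no computable change. With an assumed 30%, 50% or 70% of 200 subjects in that state, 140, 100 or 60 would remain. If it is entered as 0, all 200 remain.

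**Which daily value.** Section 15.3.6.4 also does not say which of the daily grades enters the change. A table built on the worst on-treatment grade would settle this.

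**The case against.** The strongest reply is that the plan already counts these events. Section 14.2.3 names hepatic encephalopathy among the complications to be recorded as an adverse event or serious adverse event. Section 15.1 classifies events by preferred term, severity and seriousness, and Section 15.3.6.4 reports counts and percentages. Adverse event collection also runs longer than the score: to 7 days after treatment, and to 30 days for serious events. This stands, and it means that the safety analysis as a whole does not miss new encephalopathy. It is not a full substitute. Intensity in Section 14.1.7 is mild, moderate or severe, judged by interference with activities, not by West Haven grade. Section 14.2.2 says that a deteriorating baseline condition may be considered an adverse event, which leaves progression of existing encephalopathy partly to judgment.

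Section 13.3.5 gives some further help: investigators must record the organs involved in multi-organ dysfunction and their severity, and "The use of the simplified version CLIF-C Organ Failure scoring system in documenting MODS organ involvement and MODS severity is strongly encouraged". But that applies to multi-organ dysfunction, is a recommendation as to scale, and has no planned summary in Section 15.

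A reader might infer from Table 13-3 that a subject without encephalopathy has no scorable baseline and so drops out of the analysis. The documents do not support that. Grade 0 is in Table 13-2, nothing says that an assessed absence is left blank, and the rule on missing data does not by itself make it missing. The eCRF and the site manual, which might set the code, are not among the documents. Nor can a subject both drop out as unscored and be cancelled in the mean as a +4.

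The summary is also more than a mean. The maximum would show that a coma occurred, and N would show any loss of subjects. Finally, the variable is descriptive and carries no hypothesis test, and Section 15.3.9 allows extra descriptive analyses. These points limit the size of the concern but do not supply the missing count.

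**Conclusion.** The point holds as a minor one. As planned, the summary of the encephalopathy score cannot show how many subjects per arm newly reached or worsened to grade 3-4. In the assumed examples the mean and median are 0 with anything from 2 to 10 new comas per 200, and the maximum is the same throughout. The exact zero depends on assumed offsetting improvements (4 one-grade improvements per coma from grade 0, or 3 per coma from grade 1). The absence of a count does not depend on any assumption, because it follows from the list of statistics in Section 15.3.6.4.

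It would go too far to say that the plan hides new-onset encephalopathy. Adverse event counts remain, and the missing grade 0 row is a gap in coding instructions, not evidence that such subjects are excluded. The primary analysis, alpha and power are unaffected.

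**What to change.** In Section 15.3.6.4, beside or in place of the change-from-baseline summary, add a shift table by arm of baseline grade against worst on-treatment grade. Report with it the number and percentage of subjects newly at, or worsened to, grade 3-4.

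As a supporting clarification, add a grade 0 row to Table 13-3, or a sentence in Section 13.4.2, stating that absence of encephalopathy is coded 0, consistent with Table 13-2. If grades have already been entered, check how absence was recorded and map it before the table is run.

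The cost is one table row and one extra output. The daily grades are already collected, so no assessment, visit or test is added.

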10.4 Treatment Discontinuation

- Treatment should be continued until 24 hours after 2 consecutive SCr values no more than 1.5 mg/dL have been obtained, OR up to a maximum of 14 days (maximum of 15 days if SCr first reaches 1.5 mg/dL on Day 14).
- If on Day 4 (after a minimum of 10 doses) SCr is at or above baseline value, study drug should be discontinued.
- Treatment must be discontinued when the subject is to undergo RRT, liver transplantation, TIPS or vasopressor therapy.
- Dosing must be permanently discontinued if an event of cardiac ischemia or mesenteric ischemia occurs.

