13.4.4 Adverse Events

All adverse events will be assessed and recorded beginning with study drug administration until 7 days after discontinuation of study drug. Adverse events considered serious will be assessed and recorded until 30 days after discontinuation of study drug; excluding deaths, which will be collected up to 90 days after the first dose of study drug.

Those events that are serious in nature must be reported to the sponsor or its designee for safety reporting in an expedited manner (see Section 14 for definitions and reporting requirements).

The adverse event collection schedule for the proposed study is adopted from the previous clinical studies in the same patient population and for the same drug. The time frames for collecting various types of adverse events are defined to focus on the collection of safety information pertinent to the study subjects in the proposed study, as the target patient population has an extensive health background and existing medical conditions.

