14.2 Collection of Adverse Events/Serious or Unexpected

Any AE occurring prior to signing the ICF should be considered medical history or a pre-existing condition and will be collected on the Medical History eCRF.

All AEs will be assessed and recorded beginning with study drug administration until 7 days after discontinuation of study drug and at each evaluation. Adverse events considered serious will be assessed and recorded until 30 days after discontinuation of study drug, excluding deaths, which will be collected up to 90 days after the first dose of study drug.

The investigator will collect and record all necessary data including investigations that were performed for any AE of special interest, ie, an ischemic abdominal event, ischemic cardiac event, or bronchospasm-related respiratory event.

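### Adverse events are tabulated as crude percentages over collection windows that follow treatment duration, so a drug effect on creatinine alone can move the percentages apart by a few points in either direction

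*Combined protocol and SAP*

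**What the plan says.** **Collection.** Section 13.4.4: "All adverse events will be assessed and recorded beginning with study drug administration until 7 days after discontinuation of study drug". For serious events: "Adverse events considered serious will be assessed and recorded until 30 days after discontinuation of study drug". Deaths are the exception: "excluding deaths, which will be collected up to 90 days after the first dose of study drug". Section 14.2 words the AE period slightly differently: "until 7 days after discontinuation of study drug and at each evaluation".

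**What sets the last dose.** Section 10.4 has a stop for lack of response, "If on Day 4 (after a minimum of 10 doses) SCr is at or above baseline value, study drug should be discontinued", and a stop for success, "Treatment should be continued until 24 hours after 2 consecutive SCr values no more than 1.5 mg/dL have been obtained". Otherwise dosing runs to Day 14, or Day 15 if the creatinine target is first reached on Day 14. Dialysis, transplant, TIPS or vasopressor therapy also end it.

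**Analysis.** Section 15.3.6.4: "Adverse events will be summarized by frequency and percentage of subjects". Section 15.2 promises a summary of exposure but does not link it to AE percentages. No rate per unit of time, time-to-event method or common AE window appears in the document.

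**The concern.** The denominator is subjects, but the time each subject is observed depends on creatinine response, which is the effect the trial is designed to show. If the drug works, the two arms will have different distributions of observation time. A crude percentage then mixes the risk of an event with the time available to record one.

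Safety is part of the stated objective (Section 6). The ischemic and respiratory events of special interest (Section 13.4.4.1) will be judged on differences between the arms. An artefact of a few points could suggest a harm or hide one, and the crude table would not show which.

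**Working it through.** The plan states no AE rate, stop rate or follow-up time, so there is no figure to reproduce. The check has two parts: one from the documents' rules alone, one needing assumptions.

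**1. Windows from Sections 10.4 and 13.4.4**

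| Last dose | AE window | SAE window |
|---|---|---|
| Day 4 | 4 + 7 = 11 days | 4 + 30 = 34 days |
| Day 14 | 14 + 7 = 21 days | 14 + 30 = 44 days |
| Day 15 | 22 days | 45 days |

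At one constant hazard, a 21-day AE risk of 30% appears as 1 - 0.70^(11/21) = 17.0% in 11 days. A 44-day SAE risk of 30% appears as 1 - 0.70^(34/44) = 24.1% in 34 days.

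**2. Arm level**

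Model: the same constant hazard h in both arms. A share f stops on Day 4, a share r reverses with last dose on Day t, and the rest go to Day 14. With k = 7 (AE) or 30 (SAE):

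P = f[1 - exp(-h(4+k))] + r[1 - exp(-h(t+k))] + (1 - f - r)[1 - exp(-h(14+k))]

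Inputs:
- r = 12.5% for placebo is the rate in Table 15-2.
- r = 28.5% for terlipressin is assumed. The stated 89.76% power with 12.5% on placebo implies about 27.3% (unpooled variance) to 29.4% (pooled).
- Assumed, with no source in the documents: f = 40-60% placebo and 25-30% terlipressin; t = Day 5-9; h = 1-5% per day.

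AEs at h = 0.05. Event probabilities by window: 11 days 42.31%, 12 days 45.12%, 16 days 55.07%, 21 days 65.01%.
- *Low end* (f = 40% vs 30%, t = 5). Placebo: 0.40×42.31 + 0.125×45.12 + 0.475×65.01 = 53.4%. Terlipressin: 0.30×42.31 + 0.285×45.12 + 0.415×65.01 = 52.5%. Gap **-0.9 points**.
- *High end* (f = 60% vs 30%, t = 9). Placebo: 0.60×42.31 + 0.125×55.07 + 0.275×65.01 = 50.1%. Terlipressin: 0.30×42.31 + 0.285×55.07 + 0.415×65.01 = 55.4%. Gap **+5.2 points**.
- *Far corner* (f = 60% vs 25%, t = 9). Terlipressin: 0.25×42.31 + 0.285×55.07 + 0.465×65.01 = 56.5%. Gap +6.4 points.

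SAEs at h = 0.02. Probabilities: 34 days 49.34%, 35 days 50.34%, 39 days 54.16%, 44 days 58.52%.
- *Low end* (40% vs 30%, t = 5): 53.4% terlipressin vs 53.8% placebo, **-0.4 points**.
- *High end* (60% vs 30%, t = 9): 54.5% vs 52.5%, **+2.1 points**. The far corner (60% vs 25%) gives +2.5.

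A middle case for AEs (f = 50% vs 25%, t = 7, 21-day risk 30%):
- Mean window, placebo: 0.50×11 + 0.125×14 + 0.375×21 = 15.1 days.
- Mean window, terlipressin: 0.25×11 + 0.285×14 + 0.465×21 = 16.5 days.
- Crude percentages: 22.4% placebo and 24.2% terlipressin, a gap of +1.8 points.

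**3. Control check.** With f = 40%, r = 12.5% and t = 7 in both arms, and a 21-day risk of 30%, both show 23.7%. The gap needs a drug effect on creatinine.

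**4. The other reading of the AE window.** Table 13-1 has AEs recorded through the active study period and on to 7 days after treatment. Section 13.2.3.1 runs that period to Day 14 or discharge. An inpatient who stops on Day 4 may then have about 14 AE days. With every window at least 14 days (probability 50.34% at h = 0.05):
- *High end*: 0.30×50.34 + 0.285×55.07 + 0.415×65.01 = 57.8% minus 0.60×50.34 + 0.125×55.07 + 0.275×65.01 = 55.0%, or +2.8 points.
- *Low end*: 0.585×50.34 + 0.415×65.01 = 56.4% minus 0.525×50.34 + 0.475×65.01 = 57.3%, still -0.9 points.

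**The case against.** Several objections have force.

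- **The artefact does not arise under a fully inert drug.** A reader might infer that the arms would differ even if terlipressin did nothing. They would not: stopping times would then have the same distribution in both arms. What holds is narrower: no effect on the AE hazard, but an effect on creatinine.
- **No AE test is planned.** The section promises a summary, so an inflated type I error should not be inferred.
- **Day 4 does not end treatment for every non-responder.** The rule covers creatinine at or above baseline. Under Section 10.3.2 a subject whose creatinine has fallen by less than 30% continues.
- **The direction is open.** A reader might infer that crude percentages must overstate harm on terlipressin. Early stops after reversal, expected more often on terlipressin, pull the other way and can cancel the Day 4 effect.
- **Some protection exists.** Deaths have a fixed window, exposure is summarized, a DSMB reviews safety data, and Section 13.4.4 says the collection schedule was adopted from the earlier studies of this drug.
- **A rate per subject-day is not a clean remedy.** It assumes a roughly constant hazard, while the window pools dosing days with 7 or 30 off-drug days in differing proportions.

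These points limit the size and wording of the concern. They do not remove it: no analysis in the plan separates event risk from observation time for AEs or SAEs.

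**Conclusion.** The point holds in limited form. Crude AE and SAE percentages are taken over windows whose length depends on creatinine response, so an effect on creatinine alone can separate the arms. Under the assumptions above the gap is about -1 to +5 points for AEs and -0.4 to +2 for SAEs, slightly more at the far corner. The upper end for AEs falls to about +3 (+3.5 at the far corner) if collection runs to Day 14 or discharge. Stop rates, responder timing and hazards are all assumed, so these figures show scale and are not predictions. The consequence is a descriptive table that is harder to read. Neither a false-positive test nor a bias in a known direction follows from the documents. Mortality is unaffected. A more detailed analysis plan, if one exists, was not available.

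**What to change.** In Section 15.3.6.4:

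1. Keep the crude table.
2. Add SAEs, including serious AEs of special interest, over a common window from first dose to Day 30. Collection to 30 days after the last dose already covers this for every treated subject still in follow-up. This is the soundest addition. Non-serious events have no comparable window, since a subject dosed only on Day 1 is covered to Day 1 + 7 = Day 8.
3. As a supplement, report subjects with an event per 100 subject-days at risk, counted to the first event or the end of observation, for AEs, SAEs and AEs of special interest. State beside it that the rate assumes a roughly constant hazard across on-drug and off-drug days.
4. Reconcile the AE window in Table 13-1 with Sections 13.4.4 and 14.2, so that the end of collection is the same in all three.

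Deaths need no change, and neither do the treatment rules. The cost is a few more safety tables from data already collected, plus the constant-hazard assumption behind item 3.
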